Title: Effects of Catheter Location on Postoperative Analgesia for Continuous Adductor Canal and Popliteal-Sciatic Nerve Blocks

Clinicaltrials.gov: NCT02523235

Date (text originally created): June 28, 2015

Date (document compiled from previously-created documents): July 22, 2019

RESEARCH DESIGN AND METHODS

This will be a single-center (UCSD), randomized, controlled investigation.

Enrollment. Consenting adults undergoing knee arthroplasty or foot/ankle surgery with a planned adductor canal or popliteal perineural catheter, respectively, will be offered enrollment. Study inclusion will be proposed to eligible patients prior to surgery. If a patient desires study participation, written, informed consent will be obtained using a current UCSD IRB-approved ICF. Selection for inclusion will not be based on gender, race, or socioeconomic status. Inclusion and exclusion criteria are listed in section #10 below.

Preoperative Procedures. Following written, informed consent, we will record baseline anthropomorphic information (age, sex, height, and weight) that is already provided by all patients having surgery. All subjects will have a peripheral intravenous (IV) catheter inserted, standard noninvasive monitors applied, supplemental oxygen administered via a nasal cannula or face mask, and positioned supine (adductor canal) or prone (popliteal-sciatic). Midazolam and fentanyl (IV) will be titrated for patient comfort, while ensuring that patients remain responsive to verbal cues. The area that will be subsequently covered by the catheter dressing will be clipped of hair, if necessary. The ultrasound will be placed to visualize the short axis (cross-section) of the adductor canal or popliteal regional at both proximal and distal locations. If both sites are acceptable for catheter insertion, the subject will be randomized using a computer-generated list (blocks of 8) to one of two treatment groups in a 1:1 ratio using sealed, opaque, consecutively numbered envelopes stratified by catheter type (adductor canal vs. popliteal-sciatic): (1) proximal vs (2) distal insertion.

Catheter insertion. Catheter insertion will adhere to current UCSD standard-of-care. The only difference for subjects participating in the study (vs those not participating) will be that the specific catheter insertion location—both currently standard-of-care and used daily at UCSD because of clinical equipoise—will be determined randomly, instead of the physician simply choosing him/herself. All catheters will be placed by a regional anesthesia fellow or resident under the direct supervision and guidance of a regional anesthesia attending (or by the attending him/herself). All catheters will be placed using standard UCSD perineural catheter techniques, nerve in short-axis, ultrasound-guidance.

The area of insertion will be cleaned with chlorhexidine gluconate and isopropyl alcohol (ChloraPrep One-Step, Medi-Flex Hospital Products, Inc., Overland Park, KS, USA), and a clear, sterile, fenestrated drape applied. The ultrasound probe will be placed to visualize the short-axis (cross-section) of the target nerve(s). A skin wheal will be raised at the catheter-placement needle's anticipated point of entry (proximal or distal location). A 17 gauge needle (FlexTip, Teleflex Medical, Triangle Research Park, NC, USA) will be used to place all perineural catheters. The catheter-placement needle will be inserted through the skin wheal, advanced in-plane beneath the US transducer and directed to the target nerve as described below:

Adductor canal.

Proximal: Inserted as described by Jæger et al., 2013:6

“...we performed an ultrasound survey at the medial part of the thigh, halfway between the superior anterior iliac spine and the [superior border of the] patella. In a short axis view, we identified the femoral artery underneath the sartorius muscle, with the vein just inferior and the saphenous nerve just lateral to the artery.”

Distal: Inserted as described by Manickam et al. 2009:7

“The transducer was initially placed on the medial aspect of the distal third of the thigh to identify the femoral artery immediately deep to the sartorius muscle. The transducer was then moved caudally along the long axis of the thigh until the femoral artery was seen diving deep and moving away from the anterior muscle plane (sartorius and vastus medialis muscles), toward the posterior aspect of the thigh where it becomes the popliteal artery. This area was identified as the adductor hiatus, and the block location was selected 2 to 3 cm proximally to this area, in the distal adductor canal.”

Saline (10 mL) will be administered via the needle to dilate the space where the catheter is to be inserted. A flexible non-stimulating perineural catheter (FlexTip, Arrow International, Reading, PA, USA) will be inserted 3-5 cm past the needle tip; and the needle withdrawn over the catheter. A 30 mL bolus of lidocaine 2% with 1:400,000 of epinephrine will then be administered through the catheter. A “successful” catheter insertion will be defined as decreased sensation to cold within the distribution of the saphenous nerve.

Popliteal-sciatic. Using an ultrasound, the bifurcation of the sciatic nerve will be identified in short axis and marked at a point immediately distal at which point the two main branches of the sciatic nerve are separate and a hypoechoic area can be viewed between the two. This level will be marked on the skin.

Proximal: The needle will be inserted to intersect the sciatic nerve 6-7 cm proximal to the mark on the skin (therefore, proximal to the sciatic bifurcation) and injection with saline used to ensure subepimyseal spread.

Distal: The needle tip will be inserted into the hypoechoic area between the two branches of the sciatic nerve immediately distal to the sciatic nerve bifurcation between the paraneurium and epineurium (the subparaneurial space/compartment).⁸ As described by Tran et al:⁹ “An adequate position was defined as the presence of circular expansion of the paraneurial sheath... Once circular expansion was obtained, we injected. During the injection process, the Tuohy needle was kept stationary and care was taken to ensure that neural swelling did not occur. The latter was defined as an increase in the cross-sectional surface of the nerve.⁶ If neural swelling was detected by US, the needle was carefully withdrawn before resuming the injection.”

A 40 mL bolus of normal saline or lidocaine 2% with 1:400,000 of epinephrine will then be given through the needle. A flexible non-stimulating perineural catheter (FlexTip, Arrow International, Reading, PA, USA) will be inserted 3-5 cm past the needle tip; and the needle withdrawn over the catheter. If saline was administered pre-operatively, then the 40 mL of lidocaine 2% with 1:400,000 of epinephrine will be administered through the catheter following surgery. A "successful" catheter insertion will be defined as decrease in cutaneous sensation to cold on the plantar aspect of the foot.

Intraop: Patients may receive a general and/or neuraxial anesthetic that would be determined by the intraoperative anesthesia provider. Additional boluses of 10 mL 2% lidocaine with epinephrine may be given, if needed, via the perineural catheter.

Perineural infusion: An infusion pump will be attached to each subject's perineural catheter. The pump will provide ropivacaine 0.2% at 8 mL/h (adductor) or 6 mL/h (popliteal) basal rate infusion and a 4 mL patient-controlled bolus with a 30 minute lockout (all standard at UCSD).

Data collection: All data collection will be through standard UCSD nursing/therapy EPIC notes (adductor canal) or postoperative phone calls (popliteal) for the day following surgery.

Primary endpoint: The primary endpoint will be the average pain on post operative day 1 following surgery as measured on a numeric rating scale (0-10, 0=no pain, 10=worst imaginable pain) during the time periods of 08:00-24:00 (adductor) or the two hours preceding the data-collection phone call (popliteal).

Secondary endpoints: Popliteal subjects will be called the day following surgery to collect information regarding surgical pain (Numeric Rating Scale of 0 to 10, with "0" being no pain and "10" being the worst pain ever experienced), analgesic use (oral, IV, and infusion boluses), infusion side effects, and distance ambulated (adductor catheters only). Popliteal subjects will be called one week (+/- 1 day) following surgery to inquire about possible block-related complications.

Sample size estimates:

Adductor canal. The primary analysis will utilize the Wilcoxon Rank Sum test. The figure below shows the estimated density of post-op day 1 pain scores following Proximal insertion (mean = 4.12, SD = 1.74) based on published data.¹⁰ To simulate power, we used the truncated Gaussian distribution with range 0 to 10; SD=1.74; Proximal group mean = 4.12; and Distal group means = 5, 5.5, 6, 6.5, 7, 6.5, and 8.

Under these assumptions and two-sided $\alpha = 5\%$, we simulated 10,000 trials with sample size of 25 per group with a primary end point measurement.

We found the simulated power to be as plotted below.

So we have 80% power to detect group differences in pain as small as about 1.52.

Popliteal-sciatic. Using an expected NRS mean=2.6 and SD=2.1 of average pain on postoperative day 1 (based on unpublished data from IRB study #101282), approximately 31 subjects in each treatment arm with a primary end point measurement will be required to detect a difference between treatment group means of 1.5. This is with a 2-sided alpha=0.05, beta=0.2, and power=0.8 (ClinCalc.com accessed June 28, 2015). We will employ a t-test for parametric data and Wilcoxon Rank Sum test for non-parametric data.

With the two locations combined, we will need 112 subjects with a primary end point measurement; and, we will enroll up to 150 subjects to account for drop-outs and subjects without a primary end point measurement.

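### Cheap improvement: replacing blocks of 8 with varying sizes 6, 8 and 10 cuts allocations certain to a full-tally observer from about 19% to about 1.7%; the best-guess rate stays near 66%

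*Combined protocol and SAP*

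**What the plan says.** In the Combined protocol and SAP, Preoperative Procedures, the proximal and distal sites are first examined by ultrasound. Then: "If both sites are acceptable for catheter insertion, the subject will be randomized using a computer-generated list (blocks of 8". Allocation is 1:1 from "sealed, opaque, consecutively numbered envelopes stratified by catheter type". One block size is named. The text mentions neither variation in size nor withholding of the size. The word fixed does not appear, but it is the natural reading. The opening of Research Design and Methods describes a single-center trial.

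Under Catheter insertion, "All catheters will be placed by a regional anesthesia fellow or resident under the direct supervision and guidance of a regional anesthesia attending"; an attending may also do so unaided. The insertion site is the treatment, so whoever places the catheter knows the arm. The same section describes the two sites as "both currently standard-of-care and used daily at UCSD because of clinical equipoise".

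Sample size estimates gives the stratum sizes. For the adductor canal, "we simulated 10,000 trials with sample size of 25 per group with a primary end point measurement". For the popliteal-sciatic block, "approximately 31 subjects in each treatment arm with a primary end point measurement will be required". The combined target is 112 subjects with a primary endpoint measurement, and "we will enroll up to 150 subjects to account for drop-outs and subjects without a primary end point measurement".

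**The concern.** Sealed, opaque envelopes hide the next card. They do not hide what earlier cards in the same block imply. Once four of one arm have been used in a block of 8, every remaining card in that block is known to anyone who has kept count and knows the size.

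This matters because a discretionary step comes between consent and randomization. If the person judging whether both sites are acceptable could deduce the next arm, a consented patient could be ruled out because of that arm, and the envelopes would not prevent it. At stake is the comparability of the arms at entry. The documents give no basis for expressing any resulting bias in pain-score points.

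**Working it through.** **Inputs.** Block size 8, ratio 1:1 and two strata come from Preoperative Procedures. Stratum sizes come from Sample size estimates: 2 × 25 = 50 adductor and 2 × 31 = 62 popliteal.

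**The plan's own figures.** For the popliteal stratum, n per arm = 2 × (1.960 + 0.842)² × 2.1² / 1.5² = 30.8, which rounds up to 31 as stated. The total is 50 + 62 = 112, also as stated. The plan gives no predictability figure.

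**Fixed blocks of 8, complete tally, size known.** Position k is certain when four of one arm are already used:

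P(k) = 2 × C(k−1, 4) / C(8, 4), with C(8, 4) = 70.

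| Position | 1–4 | 5 | 6 | 7 | 8 |
|---|---|---|---|---|---|
| P(certain) | 0 | 2/70 = 0.029 | 10/70 = 0.143 | 30/70 = 0.429 | 70/70 = 1 |

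- Sum per block: 112/70 = 1.6.
- Stratum of 50 (6 blocks and 2 patients): 6 × 1.6 + 0 = 9.60.
- Stratum of 62 (7 blocks and 6 patients): 7 × 1.6 + 0.029 + 0.143 = 11.37.
- Total: 20.97 of 112 = 18.7%. Over possible lists, the central 95% is 16 to 27.
- If all 150 are randomized, the split by stratum is not given. At an assumed 67/83: 8 × 1.6 + 10 × 1.6 = 28.8. At an assumed 75/75: 2 × 9 × 1.6 = 28.8. Both are 19.2%. The 3 patients left over in each stratum add nothing.

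**Incomplete tally.** The documents do not say how much one person sees, so this range is assumed. Suppose each earlier allocation is seen independently with probability q and the block position is known. The observer must have seen all four of the exhausted arm, so the total is multiplied by q⁴.

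| Share seen, q | q⁴ | Certain, of 112 | Certain, of 150 |
|---|---|---|---|
| 1 | 1 | 21.0 | 28.8 |
| 0.9 | 0.656 | 13.8 | 18.9 |
| 0.75 | 0.316 | 6.6 | 9.1 |
| 0.5 | 0.0625 | 1.3 (1.2%) | 1.8 (1.2%) |

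**Varying sizes.** This was simulated for an observer with a complete tally who knows the set of sizes and their equal weights, but not their order. The observer updates the probability of the next arm after every allocation. Results are for strata of 50 and 62.

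| Measure | Fixed 8 | 6/8/10 |
|---|---|---|
| Certain | 18.7% (21.0) | about 1.7% (1.9) |
| At least 90% sure | 18.7% | about 3.5% |
| At least 75% sure | about 26% | about 26% |
| Best guess correct | about 66% | about 66% |

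With fixed 8 the first two rows agree because the surest guess short of certainty is 4/5, after three of one arm open a block. For 150 patients, 6/8/10 leaves about 2.4 to 2.5 certain (1.6% to 1.7%).

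The gain depends on the set chosen. With 4/6/8 about 2.3% are certain and the best-guess rate rises to about 68%. With 6/8 about 4.1% are certain. Over all sets tried, the certain share ran from 0.7% (five sizes, 4 to 12) to 10.9% (2/4).

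**Balance.** The largest possible arm difference in a stratum rises from 2 to 4 at 50 or 62, and from 3 to 5 at 67 or 83. The chance of a difference above 2 in a stratum is 0 with fixed 8 against 1.0% with 6/8/10 at 50 or 62, and 14.3% against 7.7% at 67 or 83. Averaged over stratum sizes 50 to 90 it is 3.8% against 4.3%. The efficiency loss from a difference d among n is (d/n)²: (4/50)² = 0.64% and (5/67)² = 0.56%.

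**The case against.** The strongest case against is that the premise is not in the documents. The randomization sentence is passive. It does not say who judges acceptability, who opens the envelope or who knows the block size. Several operators place catheters, and no one person is shown to see every allocation in a stratum. Both sites are also in daily use outside the trial, so watching placements is not a tally: the observer must know which patients were randomized and in what order. All of this stands. It is why 19% is an upper bound on knowledge and why the half-seen figure of about 1% is given beside it.

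A second objection is that counting certain allocations flatters the change. Someone willing to act on a good guess gains or loses almost nothing, since the best-guess rate and the share at least 75% sure do not move. This also stands and limits the claim to certain and near-certain knowledge.

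Third, the plan already has a computer-generated list, a fairly large block, sealed envelopes and stated equipoise, so the choice might be called a preference. That is a reason to rank the point low. It does not remove the case for a change that costs so little.

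Fourth, the text is a compilation, and the Enrollment section says "Inclusion and exclusion criteria are listed in section #10 below", which is not supplied. List custody, withholding of the block size or a log of exclusions may be described elsewhere. Their absence here should not be read as an omission from the plan.

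**Conclusion.** The point holds as a low-priority improvement, to be considered. If blocks are fixed at 8, a person who knows the size and holds a complete tally could deduce on average about 19% of allocations with certainty (21 of 112, or 29 of 150 under the assumed splits). With half of the earlier allocations seen the share is about 1%. Equal-weight sizes 6, 8 and 10 reduce the full-tally share to about 1.7%, even if the set of sizes is known.

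A reader might infer that allocations were foreseen, that patients were selected by arm, or that concealment failed. The documents support none of these: they do not show that anyone knew the size or kept a tally. Nor should a reader infer that varying blocks make the sequence unpredictable, because the best-guess rate stays at about 66%. The 1.7% belongs to the 6/8/10 recipe and is not a property of varying blocks in general.

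**What to change.** Generate the list with block sizes 6, 8 and 10, drawn at random with equal weights within each stratum. Have this done by someone who does not place catheters, and withhold the sizes and their order from those who judge acceptability. Avoid 4/6/8, which makes the best guess slightly better than with fixed 8. If it is not already provided for elsewhere, keep a short log of each consented patient excluded at the acceptability step, with the reason, so that this step can be checked.

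The cost is a new list and envelopes, a one-line protocol change and the log. The largest possible arm difference per stratum can rise by about 2 patients, at an efficiency cost below 1%, so planned size and power are essentially unaffected.

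### Does the popliteal comparison mix catheter level with insertion technique, so that its result cannot be called an effect of location?

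*Combined protocol and SAP*

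**What the plan says.** The title is "Effects of Catheter Location on Postoperative Analgesia for Continuous Adductor Canal and Popliteal-Sciatic Nerve Blocks". Under Preoperative Procedures the two groups are "1) proximal vs (2) distal insertion", allocated 1:1 and stratified by catheter type. The Catheter insertion section says that "the specific catheter insertion location—both currently standard-of-care and used daily at UCSD because of clinical equipoise—will be determined randomly", in place of the physician's own choice.

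The Popliteal-sciatic section then describes each arm.

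- **Proximal:** "The needle will be inserted to intersect the sciatic nerve 6-7 cm proximal to the mark on the skin", which the plan notes is above the bifurcation, with "injection with saline used to ensure subepimyseal spread".
- **Distal:** the needle tip goes into the gap between the separated branches, just below the bifurcation, "between the paraneurium and epineurium (the subparaneurial space/compartment". A passage quoted from a cited study adds: "An adequate position was defined as the presence of circular expansion of the paraneurial sheath". The same passage has a check for nerve swelling during injection.

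The rest of the popliteal procedure (bolus, catheter type, depth of catheter advancement, test of success) is written without distinguishing the arms.

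**The concern.** The label names one factor, location, but the arm descriptions seem to vary three: the level along the nerve, the named spread target, and the criterion for adequate position. The term subepimyseal occurs once and is not defined, so a reader cannot tell whether it means a compartment other than the subparaneurial one.

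If all three differ, each is fully aligned with arm. A popliteal difference reported under the title's label might then be taken as the effect of moving the catheter up or down the leg, when the injection target had contributed. A null result would be open to the same doubt, since opposing components could cancel. The stratum concerned is the larger of the two.

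**Working it through.** **1. The plan's own figure.** Inputs from Sample size estimates: difference 1.5, SD 2.1, two-sided alpha 0.05, power 0.80.

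- Normal approximation: n per arm = 2 × (1.960 + 0.842)² × 2.1² / 1.5² = 30.8, so 31. This matches the plan.
- Standard error at 31 per arm = 2.1 × √(2/31) = 0.533. Power = Φ(1.5/0.533 − 1.96) = 0.803; by t-test it is 0.790.
- Stratum share: 2 × 31 = 62 popliteal and 2 × 25 = 50 adductor, total 112, as stated. 62/112 = 55.4%. This is the size of the stratum, not an estimate of bias.

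**2. Can level and technique be separated?** No. With one indicator for level and one for technique, identical across the 62 subjects, the design matrix (intercept, level, technique) has rank 2 for 3 parameters. Only the sum of the two effects can be estimated. A larger sample or covariate adjustment would not alter that.

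**3. Does this affect the planned test?** The test concerns the sum. Assume additive components and split the 1.5 points as level + technique in three ways, chosen to span the range because the documents give no split:

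| Level | Technique | Total | Power (normal) | Power (t) |
|---|---|---|---|---|
| 1.5 | 0 | 1.5 | 0.803 | 0.790 |
| 0.75 | 0.75 | 1.5 | 0.803 | 0.790 |
| 0 | 1.5 | 1.5 | 0.803 | 0.790 |

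The rows agree by construction. The table shows only that the planned inference does not depend on the split.

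**4. Does the plan claim the level component?** The title and the randomisation text speak of location and insertion. In the text, the word level is used only for the skin mark made at the bifurcation. The Catheter insertion section does tie proximal and distal to the needle's entry point, so a level-only reading is possible. It then sends the needle to the nerve according to the arm descriptions, which say where the needle goes and what spread is sought. Nowhere does the plan say that other features are held constant or that a difference will be credited to level.

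**5. Are the three components really distinct?**

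- *Level and needle position.* The gap between the branches exists only where they have separated, and the proximal arm is above the bifurcation. This part of the difference comes with the site.
- *Spread target.* Two terms are used and one is undefined. The text does not establish that they name different compartments, nor that they name the same one.
- *Position check.* Both arms confirm spread by injection. The distal arm is described more fully, through a quotation. Unequal detail does not by itself prove unequal practice.

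**The case for a change.** The best case for a change is that the remedy is cheap. A few sentences would define the term, say whether the target and the position check are common to both arms, and name the popliteal contrast as one of techniques. The adductor section strengthens the case: there the arm-specific text only locates the site, and space dilation, catheter advancement, bolus and success test follow for both arms together. The popliteal section departs from that pattern. Even if the two spread terms were synonyms, the expansion criterion and the swelling check would still be written for the distal arm alone.

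Much of this stands as description. The wording is uneven, the term is undefined, and a popliteal result cannot be credited to level with everything else equal. What does not stand is the step from there to a fault in the plan. A comparison of two complete placements, each already in use, is a legitimate and practical question, and it is the one that the randomisation answers. The proposed relabelling is close to the existing group names. The feared harm lies in how a future report might be read, and the plan contains no attribution statement that would need correcting.

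**Conclusion.** The concern does not call for a change. Followed as written, the plan gives a valid randomised comparison of two popliteal insertions, with about 80% power (79% by t-test) for a total difference of 1.5 points at SD 2.1 and 31 per arm. No allocation, endpoint, test, error rate or sample-size figure would move, and the 50 adductor subjects are not involved.

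What is left is a gap in description that authors can fill sensibly: explain the undefined term, say whether the spread check was common to both arms, and report the popliteal result as proximal against distal insertion as performed, not as an effect of level alone.

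This rests on reading location as the whole placement described for each arm, which the text supports but does not spell out. It takes no view on which insertion is right. The conclusion would differ if the plan had promised to isolate level; it does not.

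### Does the unwritten choice between two popliteal bolus sequences put the proximal versus distal comparison at risk?

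*Combined protocol and SAP*

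**What the plan says.** Under Preoperative Procedures, both sites are surveyed by ultrasound and then "If both sites are acceptable for catheter insertion, the subject will be randomized", 1:1 from sealed envelopes, stratified by catheter type only. Under Catheter insertion, the skin is anesthetized at the allocated entry point, so the operator knows the arm before the needle goes in.

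The Popliteal-sciatic text then allows two routes to the same local anesthetic dose. The first step is "A 40 mL bolus of normal saline or lidocaine 2% with 1:400,000 of epinephrine will then be given through the needle". The second option is completed later: "If saline was administered pre-operatively, then the 40 mL of lidocaine 2% with 1:400,000 of epinephrine will be administered through the catheter following surgery". The adductor canal text has one sequence for everyone, a saline injection through the needle and then "A 30 mL bolus of lidocaine 2% with 1:400,000 of epinephrine will then be administered through the catheter".

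Three other statements bear on the point:

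- Catheter insertion opens with the commitment "Catheter insertion will adhere to current UCSD standard-of-care" and gives randomized location as the only departure from routine care.
- The baseline items are listed as "we will record baseline anthropomorphic information (age, sex, height, and weight").
- The Data collection paragraph reads "All data collection will be through standard UCSD nursing/therapy EPIC notes (adductor canal) or postoperative phone calls (popliteal"), and the sentence goes on to limit itself to the day after surgery.

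**The concern.** Catheter location is the only randomized contrast. Here a co-intervention, the timing and route of the first local anesthetic bolus, is left to choice at a moment when the operator can already know the allocation. If one sequence were used more often with proximal catheters and the other with distal ones, and if sequence affected day-1 pain, the popliteal comparison would carry part of the sequence effect.

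The gap is confined to the popliteal stratum, because the adductor sequence is fixed. The standard-of-care commitment does not close it, since both sequences are permitted. The listed baseline items and the content of the phone calls also would not show which sequence a subject received, so an imbalance could go unseen.

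At stake would be bias in the popliteal primary comparison of average pain on postoperative day 1, and a false-positive rate above the nominal 5%.

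**Working it through.** **Inputs.** From Sample size estimates: SD 2.1, 31 per arm, difference 1.5, two-sided alpha 0.05, power 0.8. The document gives neither the effect of sequence on day-1 pain nor the share of each sequence by arm. Both are assumptions below, shown over a range.

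**The plan's own figure.** n per arm = 2 × (1.960 + 0.842)² × 2.1² / 1.5² = 30.8, so 31, as stated. Power at 31 per arm is 0.803 by the normal formula and 0.790 by the noncentral t. The total is 2 × 25 + 2 × 31 = 112, also as stated. The concern alters none of these.

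**Size of a possible bias.** Shift in the arm difference = (difference in use between arms) × (effect of sequence on pain score). The standard error is 2.1 × √(2/31) = 0.533. Type I error is from the noncentral t with 60 df:

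| Assumed effect (points) | Assumed difference in use | Shift | Type I error |
|---|---|---|---|
| any | 0 | 0 | 5.0% |
| 0.25 | 20 percentage points | 0.05 | 5.1% |
| 0.5 | 20 percentage points | 0.10 | 5.4% |
| 0.5 | 25 percentage points | 0.125 | 5.6% |
| 1.0 | 20 percentage points | 0.20 | 6.6% |
| 1.0 | 50 percentage points | 0.50 | 15.2% |
| 1.5 | 50 percentage points | 0.75 | 28.3% |

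In reverse, a 6% error needs a shift of 0.160 points and a 10% error needs 0.354.

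- Effect 0.5: 0.160/0.5 = 32 percentage points of difference in use for 6%, and 0.354/0.5 = 71 for 10%.
- Effect 0.25: 0.160/0.25 = 64 percentage points for 6%. For 10% it would take more than 100, which is impossible.

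**How far apart the sequences are.** Each gives 40 mL of the same lidocaine and epinephrine solution, then the same popliteal ropivacaine infusion (6 mL/h basal, 4 mL patient bolus, 30-minute lockout). They differ in timing and route. The endpoint is pain in the two hours before the next-day call. None of this proves a zero effect, but nothing in the document points to a large one.

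**When the choice is made.** The text fixes when fluid is injected. It does not say when the choice is made. A choice after the envelope is opened is permitted, but so is one settled beforehand, for example from the planned anesthetic.

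**Where the sequence would be recorded.** The Data collection sentence covers the day after surgery, and the four baseline items are patient characteristics. Neither is an exhaustive list of what may be taken from the clinical record, so silence on the sequence does not show that it is unavailable.

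**What a table by arm could show.** At 50% use, the 95% half-width for a difference in use is 1.96 × √(2 × 0.25/31) = 25 percentage points. Such a table would expose a gross imbalance but could not separate a 20-point difference from chance.

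**The case for a change.** The strongest case for a change is that prevention is cheap. Having the choice settled before the envelope is opened would rule out a systematic dependence on arm whatever the sequence effect. In a simulation of 40,000 null trials with equal use in both arms, the type I error stayed at 5.2% and 5.1% for effects of 0.5 and 1.0 points. With use of 40% against 60% it was 5.5% and 6.4%. A further argument is that one definition of successful insertion serves both sequences. After lidocaine through the needle, loss of cold sensation may reflect the needle injection alone. After saline, the planned lidocaine can reach the nerve only through the catheter. Knowing the sequence would help in reading the success rates.

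It stands that the text gives no rule and names no record, and that large assumed values would produce a material error. The step to a defect does not stand. Under Intraop the protocol equally leaves general or neuraxial anesthesia, and further 10 mL lidocaine boluses, to the provider after allocation. All of this belongs to a comparison of two locations within routine care. If location itself led clinicians to one sequence, that could fairly count as part of the location effect. Advance commitment would also constrain clinical workflow and need provision for departures, so it costs more than a sentence.

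**Conclusion.** No change to the plan is called for. The protocol does not state how or when the popliteal bolus sequence is chosen relative to opening the envelope. That is missing detail about a usual-care choice, and following the plan as written is not shown to give a wrong answer. The bias is zero if use is equal in the two arms or if sequence does not affect day-1 pain. With an assumed 20-point difference in use and an effect of 0.25 to 1 point, the type I error is 5.1% to 6.6%. Rates of 15% or more arise only from assumptions, such as a 50-point imbalance with an effect of 1 point or more, for which the document offers no support.

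This rests on the plan's SD of 2.1 and 31 per arm, on assumed values for effect and use, and on the sequence being recoverable from the procedure record, which the plan does not exclude. Analysts can fill the gap by describing the sequence used by arm from that record, with the planned tests as they are. Which sequence is used is a clinical matter, and no preference is implied.
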